2.10 Power for analysis of key secondary variables

Not applicable.

2.11 Interim analysis for futility

In Cohort 1, the interim analysis for futility will be performed separately for each of the two cohorts. Interim analyses for futility for each cohort are planned when at least 28 patients in each of Cohorts 1a, 1b, 2 and 4, and 20 patients in Cohort 3 have completed at least 6 cycles of treatment (18 weeks) or have discontinued treatment earlier. Due to the expected difference in enrollment rate for each cohort, the interim analysis for the different cohorts may occur at different times. For the interim analysis and the final analysis in Cohort 2 (MET GCN ≥ 4 and

< 6), the study targets to have at least 40% of patients with MET GCN ≥ 5 and < 6. No interim analysis is planned for Cohorts 5a, 5b and 6.

The decision to stop for futility for the respective cohort at interim will be based on the probability of success (POS). POS is the probability of a positive conclusion of the study if the study continued beyond interim, (i.e., till the final analysis), given the interim observed data (x) and success among n patients. Thus,

$$\text{POS} = \text{Prob}[\text{Final observed ORR} \geq 35\% \mid x, n]$$

Minimally informative Beta distribution prior ([Neuenschwander 2008](#)) with prior mean equal to 25% will be used, i.e., the prior distribution will be Beta (0.3333, 1) for the POS calculations at the interim analysis.

The respective cohort will be stopped for futility at the interim analysis if the respective POS < 10%.

Cohort 1a, Cohort 1b, Cohort 2 and Cohort 4

With 28 evaluable patients for interim analysis in each of the Cohorts 1a, 1b, 2 and 4, if ≤ 7 responses (POS = 0.0543) are observed then the respective cohort will be stopped for futility. Further details of POS are provided in [Table 2-9](#). For each of the Cohorts 1a, 1b, 2 and 4, if at the time that the 28th patient is enrolled a minimum of 8 responders have not yet been observed, accrual in the cohort may be temporarily suspended until either the minimum number of 8 responders are observed or results of the interim analysis allow that cohort to continue.

Table 2-9 Probability of Success at the Final Analysis Based on Various Number of Responders Observed at IA for Cohort 1a, Cohort 1b, Cohort 2 and Cohort 4

Responder at IA out of 28 evaluable patients at IA	Probability of Success
≤ 5	< 0.01
6	0.0164
7	0.0543
8	0.1398
9	0.2863
10	0.4794
11	0.6766
≥ 12	> 0.83

Table 2-10 Number of Responders for Various Number of Evaluable Patients at Interim Analyses by Required Probability of Success for Cohort 1a, Cohort 1b, Cohort 2 and Cohort 4

Number of Evaluable patients at IA	Responders at IA	Probability of Success
26	6	0.0368
26	7	0.1050
27	7	0.0765
27	8	0.1829
28	7	0.0543
28	8	0.1398

Number of Evaluable patients at IA	Responders at IA	Probability of Success
29	7	0.0377
29	8	0.1044
30	8	0.0760
30	9	0.1792
31	8	0.0540
31	9	0.1369
32	8	0.0373
32	9	0.1020
33	9	0.0740
33	10	0.1739
34	9	0.0523
34	10	0.1323
35	10	0.0980
35	11	0.2152

Cohort 3

With 20 evaluable patients for interim analysis in Cohort 3 if ≤ 5 responses (POS=0.0999) are observed then the cohort will be stopped for futility. All evaluable patients at the time of the data cut-off for the interim analysis will be used to obtain the futility boundary using the POS criteria. Further details of POS are provided in [Table 2-11](#). If at the time that the 20th patient is enrolled a minimum of 6 responders have not yet been observed, accrual in the cohort may be temporarily suspended until either the minimum number of 6 responders are observed or results of the interim analysis allow the cohort to continue.

Table 2-11 Probability of Success at the Final Analysis Based on Various Number of Responders Observed at IA for Cohort 3 (MET GCN less than 4)

Responder at IA out of 20 evaluable patients at IA	Probability of Success
1	0.0001
2	0.0009
3	0.0066
4	0.0309
5	0.0999
6	0.2379
7	0.4382
8	0.6533

3 Changes to protocol specified analyses

Not applicable.

4 Additional details on implementation of statistical methodology

The sections below contain additional details on statistical methodology that will be included in Appendix 16.1.9 (Documentation of Statistical Methods) of the CSR as well as rules details on programming rules that will be followed to implement the analyses described in [Section 2](#).

4.1 Data included in the analyses

This section provides additional details to those included in [Section 2.1](#).

The primary analysis will be conducted when all treated patients in their respective cohort that is not stopped for futility have completed at least 6 cycles of treatment (18 weeks) or a patient has discontinued treatment earlier. Each analysis will include the data with an assessment date or event start date (e.g. vital sign assessment date or start date of an adverse event) prior to or on the cut-off date. For example, if the cut-off date is 30-Dec-2008, an AE starting on 30-Dec-2008 will be reported, whereas an adverse event starting on 31-Dec-2008 will not be reported.

4.2 Patient classification into analysis sets

This section provides additional details to those included in [Section 2.2](#).

Patients are excluded from the analysis populations based on the protocol deviations entered in the database and/or on specific patient classification rules as shown in [Table 4-1](#) below.

Table 4-1 Patient classification rules

Analysis Population	Additional patient classification rules leading to exclusion
Full Analysis Set	Patients who did not receive at least one dose of study drug
Safety Set	Patients who did not receive at least one dose of study drug.
Per-Protocol Set	Protocol deviations that will lead to removal of patients from Per Protocol Set (defined in Section 2.2)

4.3 Last contact date

The last contact date will be derived for patients not known to have died at the analysis cut-off using the last complete date among the following:

Table 4-2 Last contact date data sources

Source data	Conditions
Last contact date/last date patient was known to be alive from Survival Follow-up page	Patient status is reported to be alive, lost to follow-up or unknown
Start/End dates from further antineoplastic therapy	Non-missing medication/procedure term.

Source data	Conditions
Start/End* dates from drug administration record	Non-missing dose. Doses of 0 are allowed.
End of treatment date from end of treatment page	No condition.
Tumor assessment date	Evaluation is marked as 'done'.
Laboratory/PK collection dates	Sample collection marked as 'done'.
Vital signs date	At least one non-missing parameter value
Performance Status date	Non-missing performance status
Start/End dates of AE	Non-missing verbatim term

The last contact date is defined as the latest complete date from the above list on or before the data cut-off date. The cut-off date will not be used for last contact date, unless the patient was seen or contacted on that date. No date post cut-off date will be used. Completely imputed dates (e.g. the analysis cut-off date programmatically imputed to replace the missing end date of a dose administration record) will not be used to derive the last contact date. Partial date imputation is allowed for event (death)/censoring is coming from 'Survival information' eCRF.

The last contact date will be used for censoring of patients in the analysis of overall survival.

4.4 Time unit

For all derivations, a month will be calculated as $(365.25 / 12) = 30.4375$ days.

If duration is to be reported in years, duration in days will be divided by 365.25.

If duration is to be reported in months, duration in days will be divided by 30.4375.

If duration is to be reported in weeks, duration in days will be divided by 7.

4.5 Dose interruptions and dose changes

This section provides additional details to those included in [Section 2.6](#).

All calculations of dose interruptions and dose changes are based on the dose actually taken by the patient.

An interruption is defined as a 0 mg dose taken on one or more days between two non-zero dosing periods. The last zero dose of INC280 followed by permanent discontinuation are not considered as dose interruption.

What follows defines how dose interruptions will be counted in the case of multiple dose interruptions.

- If an interruption occurs consecutively for at least two days due to the same reason, then it will be counted only once (*example: If the actual dose on days 1-3 is 800 mg and actual dose on days 4-5 is 0 mg and dose interruption on days 4-5 is due to AE, then the total number of dose interruptions is 1*).
- If an interruption occurs consecutively for at least two days due to different reasons, then it will be counted for each reason (*example: If the actual dose on days 1-3 is 800 mg and*

actual dose on days 4-5 is 0 mg and dose interruption on day 4 is due to AE and dose interruption on day 5 is due to dosing error, then the total number of dose interruptions is 2).

- If an interruption occurs for more than one day due to the same reason, but the days are not consecutive, i.e. there is at least one dosing day in between, then each dose interruption will be counted as a different occurrence (*example: if the actual dose on days 1, 3 and 5, is 800 mg and actual dose on days 2 and 4 is 0mg, and dose interruptions on day 2 and 4 are both due to dosing error, the total number of dose interruptions is 2).*

A dose change is defined as a change in dosing from one record to the next, however a dose interruption will not be counted as a dose change.

Dose reductions are a subset of dose changes where the total daily dose is lower than the previous non-zero dose.

Case 1: If a patient did not receive the protocol planned dose for any reason, then this is a dose reduction (400 mg, 800 mg).

Patient ID	Start date	End date	Dose	Regimen	Reason	Reduction (derived)	Comments
0001	22/03/2017	25/03/2017	400	ONCE PER DAY	DOSING ERROR	Y	1 st administration different from protocol planned dose (800 mg)
	26/03/2017	26/05/2017	800	2 TIMES PER DAY			

Case 2: If, due to a dosing error, a patient receives higher than protocol planned dose and moves down to the planned dose then this is not a dose reduction ([800 mg, 1000 mg, 800 mg] or [600 mg, 900 mg, 600 mg] ; However if the change is directly from a higher than planned dose down to a lower than protocol planned dose, then this is a dose reduction (e.g. In the sequence [800 mg, 1000 mg, 400 mg] or [600 mg, 900 mg, 400 mg], is a dose reduction).

Patient ID	Start date	End date	Dose	Regimen	Reason	Reduction (derived)	Comments
0002	22/03/2017	21/05/2017	800	2 TIMES PER DAY			
	22/05/2017	23/05/2017	0		ADVERSE EVENT		
	24/05/2017	01/08/2017	600	2 TIMES PER DAY	ADVERSE EVENT	Y	
	02/08/2017	02/08/2017	700	2 TIMES PER DAY	DOSING ERROR		
	03/08/2017	05/08/2017	800	2 TIMES PER DAY			
	06/08/2017	06/08/2017	1000	2 TIMES PER DAY	DOSING ERROR		
	07/08/2017	12/09/2017	800	2 TIMES PER DAY		N	moves down to the dose administered just before dosing error
0003	22/03/2017	21/05/2017	800	2 TIMES PER DAY			
	22/05/2017	23/05/2017	0		ADVERSE EVENT		

Patient ID	Start date	End date	Dose	Regimen	Reason	Reduction (derived)	Comments
	24/05/2017	01/08/2017	600	2 TIMES PER DAY	ADVERSE EVENT	Y	
	02/08/2017	02/08/2017	700	2 TIMES PER DAY	DOSING ERROR		
	03/08/2017	05/08/2017	800	2 TIMES PER DAY			
	06/08/2017	06/08/2017	1000	2 TIMES PER DAY	DOSING ERROR		
	07/08/2017	12/09/2017	600	2 TIMES PER DAY		Y	moves down to a lower dose administered just before dosing error

Case 3: If due to interruption, a patient receives half of the dose during 1 day and followed by an interruption (due to the same reason) then this is not a dose reduction (for ex: 800 mg 2 times per day from 27-Dec-2016 to 14-Jan-2018, and 400 mg once per day on 15-Jan-2018 and then interruption 16-Jan-2018 to 22-Jan-2018). After interruption, dose reduction will be determined using the dose received on a day without interruption (for ex: 600 mg vs 800 mg ignoring 400 mg on 15-Jan given it is related to the interruption).

Patient ID	Start date	End date	Dose	Regimen	Reason	Reduction (derived)	Comments
0004	27/12/2017	14/01/2018	800	2 TIMES PER DAY			
	15/01/2018	15/01/2018	400	ONCE PER DAY	ADVERSE EVENT	N	½ dose for 1 day same reason than interruption Interruption started on 15-Jan
	16/01/2018	22/01/2018	0		ADVERSE EVENT		
	23/01/2018	07/02/2018	600	2 TIMES PER DAY	ADVERSE EVENT	Y	Dose reduction from 800 mg to 600 mg [400 mg on 15Jan ignored for reduction determination as part of the interruption]
	08/02/2018	19/02/2018	0		ADVERSE EVENT		
0005	25/04/2016	22/05/2016	800	2 TIMES PER DAY			
	23/05/2016	23/05/2016	400	ONCE PER DAY	ADVERSE EVENT	N	½ dose for 1 day same reason than interruption Interruption started on 23-May
	24/05/2016	25/05/2016	0		ADVERSE EVENT		
	26/05/2016	26/05/2016	400	ONCE PER DAY	ADVERSE EVENT	Y	Dose reduction from 800 mg to 400 mg [400 mg on 23May ignored for reduction determination as part of the interruption]
	27/05/2016	05/06/2016	800	2 TIMES PER DAY			
	06/06/2016	06/06/2016	400	ONCE PER DAY	DOSING ERROR	Y	

Patient ID	Start date	End date	Dose	Regimen	Reason	Reduction (derived)	Comments
	07/06/2016	01/08/2016	800	2 TIMES PER DAY			
	02/08/2016	02/08/2016	400	ONCE PER DAY	DOSING ERROR	Y	½ dose for 1 day different reason than interruption
	03/08/2016	07/08/2016	0		ADVERSE EVENT		

Case 4: If due to permanent discontinuation, a patient receives half of the dose the last day of treatment then this is not a dose reduction (for ex: 800 mg 2 times per day from 30-May-2016 to 03-Oct-2016, and 400 mg once per day on 04-Oct-2016). This rule is applied for any dose levels (for ex: 600 mg 2 times per day from 15-Dec-2017 to 20-Dec-2017, and 300 mg once per day on 04-Oct-2016).

Patient ID	Start date	End date	Dose	Regimen	Reason	Permanently discontinuation	Reduction (derived)
0006	30/05/2016	03/10/2016	800	2 TIMES PER DAY			
	04/10/2016	04/10/2016	400	ONCE PER DAY	ADVERSE EVENT	Y	N

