#### 6.1.1 Dosing regimen

INC280 tablet will be administered orally on a continuous twice daily (BID) dosing schedule, on a flat scale of mg/day and not individually adjusted by weight or body surface area. A complete cycle of treatment is defined as 21 days of twice daily treatment with INC280. The investigator must instruct the patient to take the study drug exactly as prescribed.

- Except on days of PK sampling, patients should take 400 mg INC280 tablets twice daily (BID) at approximately the same time each day starting at Cycle 1 Day 1.
- Each dose of INC280 is to be taken with a glass of water (at least 8 ounces – approximately 250 mL) and consumed over as short a time as possible (i.e., not slower than 1 tablet every 2 minutes).
- Patients should be instructed to swallow the tablets whole and not to chew them.
- INC280 should be administered in the fasted state, at least 1 hour before or 2 hours after a meal. The morning and the evening doses should be taken 12 ( $\pm$  4) hours apart, although 12-hour interval is highly recommended. The morning dose should be taken the same time each morning. If a dose is not taken within 4 hours of the planned dosing time, the missed dose should not be replaced
- Only for Cohort 6 and 7, INC280 can be administered with or without food.
- On days when PK blood samples are to be collected, patients will be instructed to hold their dose until arrival at the study center. INC280 will be administered at the site in the morning prior to the PK blood draws supervised by a member of the research team. The exact time of drug administration should be recorded in the appropriate eCRF. If a patient vomits within 4 hours of INC280 dosing, the time of vomiting should be recorded on the eCRF.
- Patients should be instructed not to make up for missed doses or partial doses (i.e., when the entire dose is not taken as instructed). A missed or partial dose will be defined as a case when the full dose is not taken within 4 hours of the scheduled twice daily dosing. If that occurs, then the dose (or part remaining dose) should not be taken and dosing should restart with the next scheduled dose. If vomiting occurs, no attempt should be made to replace the vomited dose before the next scheduled dose.
- During the whole duration of treatment with INC280, the patient is recommended to use precautionary measures against ultraviolet exposure (e.g., use of sunscreen, protective clothing, avoid sunbathing or using a solarium).

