### **6.3.2 Dose reduction and re-escalation**

An INC280 dose reduction will follow the dose reduction steps described in [Table 6-2](#). For each patient, a maximum of 2 dose level modifications is allowed after which the patient must be discontinued from treatment with INC280. The lowest dose allowed, 200 mg BID in tablets is expected to be pharmacologically active, as the observed steady state plasma trough concentrations ([\[CINC280X1101\]](#), [\[CINC280X2202\]](#), n=6) were above the concentration associated with full cMET inhibition in xenograft mice models (IC90, 120 nM total concentration).

Dose re-escalation of study treatment to the previous dose level is allowed only once, and if no AE leading to dose modification is observed after at least 1 cycle (3 weeks) of study treatment at the reduced dose.

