#### **10.5.3.5 Tolerability**

Tolerability will be summarized in terms of dose reductions or drug interruption due to an AE by cohort/sub-cohort.

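### Outside its Case 3 and Case 4 exceptions, SAP 4.5 counts isolated single-dose days and restart half-days as dose reductions, which inflates the reduction count and can label a restart half-day as AE-related

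*SAP*

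**What the plan says.** SAP 4.5 first sets the basis: "All calculations of dose interruptions and dose changes are based on the dose actually taken by the patient". It then defines the term: "Dose reductions are a subset of dose changes where the total daily dose is lower than the previous non-zero dose". An interruption needs at least one 0 mg day, so a single missed dose cannot be one. Four cases with worked dosing records follow:

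- Case 1 uses the planned dose as its reference: "If a patient did not receive the protocol planned dose for any reason, then this is a dose reduction". Its example, patient 0001, has 400 mg once per day for the first four days and is flagged.
- Case 2 covers return from a dosing-error overdose and is not at issue here.
- Case 3 opens "If due to interruption, a patient receives half of the dose during 1 day and followed by an interruption (due to the same reason" and rules that such a day is not a reduction. It adds that a reduction after the interruption is judged on a day that is not part of the interruption.
- Case 4 exempts a half dose on the last day of treatment.

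In the protocol, section 6.3.2 says "An INC280 dose reduction will follow the dose reduction steps described in" Table 6-2, whose levels are 400, 300 and 200 mg BID. Section 6.1.1 says "Patients should be instructed not to make up for missed doses or partial doses", so a missed dose leaves a day at half the planned total. Protocol 10.3 and SAP 2.6 summarize reductions with their reasons by cohort. Protocol 10.5.3.5 says: "Tolerability will be summarized in terms of dose reductions or drug interruption due to an AE by cohort/sub-cohort".

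**The concern.** A rule based on the daily total cannot tell a missed dose from a lower dose level. One 400 mg dose in a day totals 400 mg, and so does the lowest level in Table 6-2 (2 × 200 mg). A patient kept at 400 mg BID throughout can therefore appear in the exposure table as dose-reduced.

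The exceptions are also one-sided. The half-day on which an interruption begins is absorbed into it, but the half-day on which dosing resumes is not. If the restart record carries the reason for the hold, an AE hold followed by full-dose resumption adds a patient to the AE-related reduction row. A reader could also misread the listing: protocol 6.3.2 allows at most two dose level modifications per patient, and three flagged reductions in one patient would seem to exceed that limit although no dose level changed.

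**Working it through.** **Inputs.** The dosing records, reasons and derived flags for patients 0001 to 0006 in SAP 4.5. The dose column is read as the daily total, since SAP 2.6 gives the planned dose as 800 mg/day.

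**Step 1: reproduce the plan's flags.** Applying the general definition and Cases 1 to 4 to the six patients reproduces all 12 stated flags, 8 Y and 4 N. By patient, the Y counts are 0001: 1, 0002: 1, 0003: 2, 0004: 1, 0005: 3, 0006: 0.

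**Step 2: separate the half-dose records.** Seven records are once per day. Four are Y (0001 once, 0005 three times) and three are N (one each in 0004, 0005 and 0006). Of the four Y records, three have reason dosing error and one has reason adverse event.

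**Step 3: follow patient 0005 (2016).**

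| Dates | Daily dose | Regimen | Reason | SAP flag |
|---|---|---|---|---|
| 25/04–22/05 | 800 | twice | | |
| 23/05 | 400 | once | adverse event | N |
| 24/05–25/05 | 0 | | adverse event | |
| 26/05 | 400 | once | adverse event | Y |
| 27/05–05/06 | 800 | twice | | |
| 06/06 | 400 | once | dosing error | Y |
| 07/06–01/08 | 800 | twice | | |
| 02/08 | 400 | once | dosing error | Y |
| 03/08–07/08 | 0 | | adverse event | |

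Every twice-daily record is 800 mg/day, yet there are three Y flags. The SAP's comment on 26/05 reads "Dose reduction from 800 mg to 400 mg [400 mg on 23May ignored for reduction determination as part of the interruption". The half-day of 23/05 is thus set aside as part of the hold, while the half-day at the other end of the same hold is compared with 800 mg and counted. If 26/05 were treated like 23/05, the first day outside the interruption would be 27/05, and the comparison would be 800 with 800: no reduction.

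**Step 4: recount.** The fix below moves the 26/05 record into the interruption and the 06/06 and 02/08 records into a partial-dosing row, and keeps patient 0001 visible as a multi-day reduced daily dose.

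| Six example patients | SAP rule | After the fix |
|---|---|---|
| Reduction flags | 8 | 8 − 3 = 5 |
| Patients with a reduction | 5 | 5 − 1 = 4 |
| Patients with a reduction for adverse event | 4 (0002, 0003, 0004, 0005) | 3 |
| One-day partial-dosing records shown separately | none | 2 |

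Counting only falls in the twice-daily level would also remove patient 0001, giving 4 reductions in 3 patients.

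**Step 5: sensitivity to missed doses (assumption only).** If each dose is missed independently with probability m, the chance of at least one single-dose day in d days is 1 − (1 − 2m(1 − m))^d. For d = 126 (6 cycles × 21 days):

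- m = 0.1%: 1 − (1 − 0.001998)^126 = 22%
- m = 0.5%: 1 − (1 − 0.00995)^126 = 72%
- m = 1%: 1 − (1 − 0.0198)^126 = 92%

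This assumes that every miss is recorded and ignores Cases 3 and 4. It shows only that the all-reason count is sensitive to rare misses.

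**The case against.** The strongest reply is that counting the dose taken is a disclosed convention. Table 6-2 governs how investigators lower the dose, and protocol 10.3 does not tie the analysis definition to it. That stands as far as it goes, but it does not explain why the two ends of one hold are treated differently.

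Three stronger readings are tempting, and the documents do not support them:

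- A reader might infer that every single-dose day is a reduction. Cases 3 and 4 exempt some, and 3 of the 7 once-per-day example records are N.
- A reader might infer that the protocol's tolerability summary is misstated as a whole. That summary concerns reductions or interruptions due to an AE. SAP 2.6 reports reasons, so records coded dosing error (3 of the 4 flagged half-dose records) can be separated. Patient 0005 already has an AE interruption and would appear in a combined count in any case. The SAP 2.8.2 tables of AEs requiring dose adjustment are a separate output, not stated to use this flag. What remains exposed is the separate AE-related reduction row.
- A reader might infer that reduction should simply mean a lower dose per administration. That would hide sustained once-daily dosing, such as patient 0001's four days at half the planned total.

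Two further cautions stand. The SAP does not say whether the 26/05 record reflects the time of restart or a deliberate half-dose day. Case 1 is better read as an unstated extra reference (the planned dose) than as an error, although the general definition does not cover a first dose.

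**Conclusion.** The point holds in this limited form. Following SAP 4.5 as written overstates the all-reason reduction count and can place a restart half-day in the AE-related reduction row. The demonstrated size is confined to the SAP's illustrations: three of eight flags, and one of four patients with an AE-related reduction. The size in the trial cannot be derived, because neither a missed-dose rate nor a frequency of restart half-days is given. The percentages in step 5 rest wholly on an assumed rate and mainly describe the category that can be separated by reason. No efficacy endpoint or hypothesis test is touched. Cumulative dose, dose intensity and relative dose intensity do not use the flag. The change is worth making because a safety-facing table would otherwise mix partial-dose days with lowered dose levels under one label.

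**What to change.** In SAP 4.5:

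1. Extend Case 3 so that a single half-dose day immediately after an interruption, followed by return to the pre-interruption daily dose, is part of that interruption. Patient 0005's record of 26/05/2016 becomes N.
2. Tabulate isolated one-day partial dosing at an unchanged dose level separately from dose-level reductions, by reason. Patient 0005's records of 06/06 and 02/08/2016 move there.
3. Keep multi-day reduced daily dosing, such as patient 0001's, visible in the table.
4. State that Case 1 compares the first dose with the planned dose because no previous non-zero dose exists.

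The definitions of cumulative dose, dose intensity and relative dose intensity stay as they are. The cost is one more row in the exposure table and a small programming change. Dose, regimen and reason already appear in the example records, so no new data are needed.
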